1.4 UBLITUXIMAB AND UMBRALISIB (U2) COMBINATION

A Phase I/Ib dose escalation study (Study UTX-TGR-103) was conducted in B-cell (CLL and NHL) malignancies to establish the MTD of the combination of ublituximab and umbralisib (U2) and characterize safety and efficacy (NCT02006485). The study Is completed. The MTD was not reached and the most common all grade, all causality AEs in > 20% of subjects were: diarrhea (57%), nausea (53%), fatigue (43%) and neutropenia (32%) (Davids et al., 2017). The ORR for the CLL/SLL cohort was 62% in the 21 evaluable subjects with a 10% CR rate (Lunning et al., 2019). U2 was well tolerated and the safety and efficacy profile supports further research with multi-drug regimens including novel targeted agents.

The Phase 3 UNITY-CLL trial (NCT02612311) demonstrated that ublituximab and umbralisib (U2) prolonged PFS compared to the chemoimmunotherapy combination of obinutuzumab and chlorambucil in both treatment naïve and previously treated CLL populations (Gribben et al., 2020). The safety profile of the U2 combination was consistent with the profiles seen with umbralisib and ublituximab as monotherapies, and no new safety signals were identified. An interim analysis evaluated the individual contribution of umbralisib and ublituximab as single agents to the U2 combination and confirmed U2 as superior compared to either agent as a monotherapy. These data establish U2 as superior to chemoimmunotherapy; thus, making U2 an appropriate control arm in both treatment naïve and previously treated CLL.

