1.5 VENETOCLAX IN CLL

The BCL-2 family of genes encodes a family of closely related proteins that possess either proapoptotic or anti-apoptotic activity and share up to 4 BCL-2 Homology (BH) domains. In CLL, microRNAs miR15a and miR16-1 that negatively regulate the transcription of BCL-2 are deleted or down regulated, resulting in increased expression of BCL-2 (Cimmino et al., 2005). Venetoclax is an orally administered BCL-2 inhibitor demonstrating in vitro activity against primary CLL cells and in lymphoid malignancy xenograft models (Souers et al., 2013). In a Phase I dose escalation study enrolling 116 relapsed/refractory CLL patients, tumor lysis syndrome (TLS) was initially observed but decreased after a dose escalation over 5 weeks was initiated. The terminal t1/2 of venetoclax was 19 hours, allowing daily dosing. With the 5-week dose escalation and TLS precautions, only 1 of 60 U2-VEN-207

Dated: 05 October 2021 (Ver 4.0)

Page **36** of **112**

patients had laboratory evidence of TLS and no patients had clinical sequelae. Otherwise, Grade 1/2 diarrhea and nausea were observed in roughly 50% of patients as was neutropenia, reaching Grade 3/4 in 41% (Roberts et al., 2016). Of the 116 patients, the response rate was 79%, with 20% CRs. Of the 23 patients who had a CR, 17 underwent MRD testing and 6 (35%) had negative results per standard criteria. The median PFS for the 60 patients in the dose escalation was 25 months and not yet reached at 17 months in the expansion cohort (estimated to be 66% at 15 months).

Venetoclax is FDA-approved for treatment of adult patients with CLL or SLL(AbbVie, 2020). In treatment naïve CLL/SLL, the Phase 3 CLL-14 trial showed venetoclax plus obinutuzumab prolonged PFS compared to obinutuzumab-chlorambucil (Fischer et al., 2019). In the relapsed/refractory setting, the Phase 3 MURANO trial illustrated that the venetoclax plus rituximab combination improved PFS compared to bendamustine plus rituximab (Seymour et al., 2018). Furthermore, these trials highlighted the potential for time limited treatment using chemotherapy-free regimens with 12 months of venetoclax in treatment naïve CLL/SLL and 24 months of venetoclax in relapsed/refractory CLL/SLL. Both trials demonstrated that venetoclax based regimens can produce high rates of uMRD which is associated with prolonged PFS independent of radiographic response (Kater et al., 2019).

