3 ELIGIBILITY CRITERIA

3.1 INCLUSION CRITERIA

Subjects must meet all the following inclusion criteria to be eligible for participation in this study:

- 1. B-cell CLL/SLL that warrants treatment consistent with iwCLL 2018 criteria for initiation of therapy with diagnosis established according to iwCLL 2018 criteria and documented within medical records. At least one of the following criteria must be met:
 - a. Evidence of progressive marrow failure as manifested by the onset or worsening of anemia and/or thrombocytopenia; or
 - b. Massive (i.e., lower edge of spleen ≥ 6 cm below the left costal margin), progressive, or symptomatic splenomegaly; or
 - c. Massive (i.e., ≥ 10 cm in the longest diameter) or progressive or symptomatic lymphadenopathy; or
 - d. Progressive lymphocytosis in the absence of infection, with an increase in blood absolute lymphocyte count (ALC) >50% over a 2-month period or lymphocyte doubling time of <6 months; or
 - e. Constitutional symptoms, defined as any one or more of the following disease-related symptoms or signs occurring in the absence of evidence of infection:
 - i. Unintentional weight loss of ≥10% within the previous 6 months; or
 - ii. Significant fatigue (≥ Grade 2); or
 - iii. Fevers >100.5°F or 38.0°C for ≥2 weeks; or
 - iv. Night sweats for >1 month.
- 2. Adequate organ system function, independent of growth-factor or transfusion support, defined as follows:
 - a. Absolute neutrophil count (ANC) \geq 750/mm³ (μ L) / platelet count \geq 40,000/mm³ (μ L);
 - b. Total bilirubin ≤1.5 times the upper limit of normal (ULN). Subjects with Gilbert's syndrome with bilirubin > 1.5 × ULN allowed per discussion with the Medical Monitor;
 - c. Alanine aminotransferase (ALT) and aspartate aminotransferase (AST) \leq 2.5 x ULN if no liver involvement or \leq 5 x the ULN if known liver involvement;
 - d. Calculated creatinine clearance >30 mL/min (as calculated by the Cockcroft-Gault formula).
- 3. ECOG performance status ≤ 2 .
- 4. Male or female \geq 18 years of age.
- 5. Ability to swallow and retain oral medication.

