8 TREATMENT PLAN

8.1 TREATMENT SUMMARY

Treatment will be administered in 28-day cycles. Patients must continue to meet eligibility in respect to adequate organ system function as per Inclusion Criteria #2 on Cycle 1 Day 1. Hematology and chemistry results must be reviewed prior to dosing on Cycle 1 Day 1 to ensure subjects meet Inclusion Criteria #2 as per the protocol.

Please see Section 8.5.3: Guidelines for Administration of Venetoclax for specific information on TLS risk, prophylaxis and assessments.

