11.9 SAFETY ANALYSES

Safety analyses will be performed using the safety population. Safety analyses will be primarily based on the incidence, severity, and type of AEs, as well as on clinically meaningful laboratory results, physical examination, and vital signs as available. Safety variables will be tabulated and presented by the dose of ublituximab, umbralisib, and/or venetoclax actually received. Exposure to study treatment and reasons for discontinuation of study treatment will also be tabulated.

Detailed information collected for each AE will be included in a listing: AE term, start/stop dates of the AE, seriousness, severity, relationship to study drug(s), action taken, and outcome. In addition, the number and percentage of subjects experiencing at least one treatment-emergent AE will be tabulated by body system, preferred term, and CTCAE grade. Treatment-emergent AEs, drug-related AEs, AESIs, SAEs, AEs with a fatal outcome, and AEs leading to discontinuation/dose modification will be further summarized. Summary statistics for actual values and for changes from baseline will be tabulated for clinical laboratory results by scheduled visit. Subjects with laboratory values outside of the normal reference range at any post-baseline assessment will be summarized and graded per NCI CTCAE Version 5.0 as applicable. Subject incidence of abnormal laboratory results will be summarized by treatment group and maximum grade for each abnormal laboratory finding.

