12.2.3.1 ABNORMAL LABORATORY VALUES, PHYSIOLOGICAL RESULTS, AND VITAL SIGNS

Abnormal laboratory values, physiological test results (e.g., QTc prolongation in electrocardiogram [ECG]), or vital signs should not be reported as an AE unless any criterion for an SAE is fulfilled, if it results in the subject to discontinue study drug, if it is associated with an overdose, or in the Investigator's judgement the abnormality should be reported as an AE.

If an abnormal finding is associated with a clinical sign and/or symptom, the sign or symptom should be reported as an AE, and the associated laboratory value or vital sign should be considered additional information that must be collected in the relevant eCRF. If the laboratory abnormality is a sign of a disease or syndrome, only the diagnosis needs to be recorded on the SAE Report Form or AE eCRF.

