12.7 PRE-EXISTING MEDICAL CONDITIONS

U2-VEN-207

A pre-existing relevant medical condition is one that is present at the start of the study. Such conditions should be recorded on the study's appropriate medical history eCRF. A pre-existing medical condition should be recorded as an AE or SAE only if the frequency, severity, or character of the condition worsens during the study. When recording such events on the appropriate SAE Report Form and/or eCRF, it is important to convey the concept that the pre-existing condition has changed by including applicable descriptors.

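### As stated in Section 11.9, the laboratory abnormality table has no worsening-from-baseline condition, so cytopenias present at entry are counted as post-baseline incidence in both arms

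*Combined protocol and SAP*

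**What the plan says.** Section 11.9 (Safety Analyses) sets the laboratory rule in two sentences. The first decides who is counted: "Subjects with laboratory values outside of the normal reference range at any post-baseline assessment will be summarized and graded", using CTCAE v5.0. The second decides how they are shown: "Subject incidence of abnormal laboratory results will be summarized by treatment group and maximum grade for each abnormal laboratory finding". Neither refers to the baseline value. The only laboratory output in 11.9 that uses baseline is a by-visit summary of actual values and changes.

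Section 3.1 admits subjects with existing cytopenias. Inclusion 2 requires ANC of at least 750/mm3 and platelets of at least 40,000/mm3, and has no hemoglobin criterion. Inclusion 1 lists as one reason to treat: "Evidence of progressive marrow failure as manifested by the onset or worsening of anemia and/or thrombocytopenia".

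The adverse event rules do look back to baseline. Section 12.1 covers what is new or aggravated, and Section 12.7 says an existing condition "should be recorded as an AE or SAE only if the frequency, severity, or character of the condition worsens during the study". However, Section 12.2.3.1 says that an abnormal laboratory value "should not be reported as an AE unless any criterion for an SAE is fulfilled", leads to discontinuation of study drug, goes with an overdose, or is judged reportable by the investigator.

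Section 11 opens by leaving analysis detail to a Statistical Analysis Plan, and Section 11.10 refers to it again. The text of that plan is not supplied.

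**The concern.** Onset or worsening of anemia or thrombocytopenia is one of the listed reasons to treat, so some subjects will be cytopenic before the first dose. A table that counts any out-of-range post-baseline value then mixes two things: cytopenia the subject brought into the trial, and cytopenia that arose or deepened on treatment. A subject who enters abnormal and only improves is still counted.

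Venetoclax is the drug that separates the two arms, and Section 1.5 reports neutropenia in roughly half of the patients in a venetoclax study. Readers will look at the hematology rows to judge what it adds to U2. Carried-over cytopenias raise the count in both arms and pull the ratio of the two rates toward 1, so added hematologic toxicity would look relatively smaller than it is.

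**Working it through.** The plan gives no figure that depends on this rule, so there is nothing to reproduce. The check follows the rule through the schedule and then illustrates its effect.

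**Step 1: who is counted.** Table 5 (Section 6) repeats hematology on Cycle 1 Day 2. Take a subject who enters with platelets at the 40,000/mm3 floor, is still below range on Day 2 and is normal at every later visit. That subject meets the 11.9 rule and is shown at the worst post-baseline grade, although the count never fell below its entry level. The same holds for neutrophils above the 750/mm3 floor and for hemoglobin at any level. A subject who is back in range at the first post-baseline check and stays there is not counted.

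**Step 2: formulas.** Let
- b = share abnormal at entry, equal in the two arms;
- p = rate of new abnormality among the others;
- w = rate of further worsening among those abnormal at entry.

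Assume that everyone abnormal at entry has at least one out-of-range value afterwards. Then
- rate as written = b + (1 − b)p;
- rate with a worsening rule = (1 − b)p + bw.

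The excess in each arm is b(1 − w).

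**Step 3: inputs.** The documents do not give b; 5%, 10% and 20% are assumed. For p, the all-grade neutropenia rates quoted in the protocol are used purely as illustrations: about 50% (Section 1.5, venetoclax in relapsed or refractory CLL) and 32% (Section 1.4, U2 in CLL and NHL). Their ratio is 0.50/0.32 = 1.56 and their difference is 18.0 points. Two cases for w are taken: none worsen (w = 0), or they worsen as often as the others (w = p). The ratio with a worsening rule is 1.56 in both cases.

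**Step 4: results as written.**

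| b | p = 50% | p = 32% | Ratio | Difference |
|---|---|---|---|---|
| 5% | 0.05 + 0.95 × 0.50 = 52.5% | 0.05 + 0.95 × 0.32 = 35.4% | 1.48 | 17.1 points |
| 10% | 0.10 + 0.90 × 0.50 = 55.0% | 0.10 + 0.90 × 0.32 = 38.8% | 1.42 | 16.2 points |
| 20% | 0.20 + 0.80 × 0.50 = 60.0% | 0.20 + 0.80 × 0.32 = 45.6% | 1.32 | 14.4 points |

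**Step 5: share of the count that only reflects entry status.** The share is b(1 − w) divided by the rate as written.
- w = 0, b = 5%: 0.05/0.525 = 9.5% and 0.05/0.354 = 14.1%.
- w = 0, b = 10%: 0.10/0.550 = 18.2% and 0.10/0.388 = 25.8%.
- w = 0, b = 20%: 0.20/0.600 = 33.3% and 0.20/0.456 = 43.9%.
- w = p, b = 10%: 0.10 × 0.50/0.550 = 9.1% and 0.10 × 0.68/0.388 = 17.5%.

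**Step 6: risk difference.** With w = 0 the excess b is the same in both arms, so the difference does not change. With w = p the worsening rule gives 18.0 points, so the table as written understates it by 0.9, 1.8 and 3.6 points.

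**Step 7: higher grades.** With purely assumed rates of 25% and 12% in a Grade 3 or higher row (ratio 2.08), the same formula gives ratios of 1.93, 1.75 and 1.56 when 2%, 5% and 10% already have that grade at entry.

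**The case against.** The best reply is that detail is left to a Statistical Analysis Plan, and that treatment-emergent laboratory rules and shift tables are the sort of content it would hold. This stands as a limit. A reader might infer that the trial has no worsening rule anywhere; the documents do not support that, because the plan's text is not supplied. It does not remove the point, because 11.9 is not silent: it states a counting rule, and that rule needs changing or qualifying.

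A second reply is that 11.9 never calls the laboratory table treatment-emergent, so a worst post-baseline grade table is correct as labelled. That is true of the label. It still leaves the reader unable to separate entry cytopenia from on-treatment cytopenia.

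A third is that other outputs cover the gap: by-visit changes, listings, treatment-emergent adverse events, and dose holds for severe cytopenias. They limit the loss but do not repair the table. By-visit changes do not show which counted subjects entered abnormal, and Section 12.2.3.1 keeps many isolated laboratory values out of the adverse event tables.

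A fourth is that the figures are not evidence about this trial. This stands. Prevalence at entry is assumed, the two rates come from different studies (the 32% is an adverse event rate, not a laboratory rate), neither is from U2-V, and they concern neutropenia whereas the qualifying criterion names anemia and thrombocytopenia.

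A reader might also suppose that the effect is confined to any-grade and lower-grade rows. The documents do not support this either. With no hemoglobin floor, no anemia grade is excluded at entry, and the CTCAE cut-offs needed to translate the neutrophil and platelet floors into grades are not given.

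**Conclusion.** The point holds for the rule stated in 11.9. Cytopenias present at entry and still out of range at one later check are counted. This inflates incidence in both arms and blurs the hematology contrast in any grade the floors permit, including all anemia grades.

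The size in this trial is unknown. The illustrated fall in the ratio, from 1.56 to between 1.48 and 1.32, rests on the assumed 5% to 20% abnormal at entry, equal prevalence in the two arms, and borrowed neutropenia rates.

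The consequence is limited. Phase 3 is randomized, so a reader who inferred a spurious difference between arms would be going too far; the risk difference moves by at most 3.6 points in the illustration. Section 11.9 bases safety primarily on adverse events. No formal test or planned ratio uses the table, and the stopping rules in 11.11.5 use treatment-related Grade 5 events and discontinuations. Nothing is claimed for ALT, AST or bilirubin, because how CTCAE v5.0 grades an abnormal baseline is not in the documents. Severity is low: a cheap improvement rather than an error that threatens a conclusion.

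**What to change.** In 11.9 or the Statistical Analysis Plan:

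- Count a laboratory abnormality as treatment-emergent only if it is at least one CTCAE grade worse than the last pre-dose value.
- Report incidence and maximum grade on that basis, by arm within each cohort.
- Add baseline-to-worst-grade shift tables for ANC, platelets and hemoglobin.

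If the Statistical Analysis Plan already contains this rule, a cross-reference in 11.9 is enough.

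No new data are needed, since Section 8.1 already requires the pre-dose values: "Hematology and chemistry results must be reviewed prior to dosing on Cycle 1 Day 1 to ensure subjects meet Inclusion Criteria #2". The cost is a change of wording and a little extra programming, and it can be made at any time up to reporting.

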11.10 MISSING VALUE HANDLING PROCEDURES

In general, other than for partial dates, missing data will not be imputed and will be treated as missing. The algorithms for imputation of partial dates vary depending upon the parameter and are presented in the Statistical Analysis Plan.

11.11 STATISTICAL ANALYSES

11.11.1 PRIMARY EFFICACY VARIABLES

11.11.1.1 PROGRESSION-FREE SURVIVAL (PHASE 3)

PFS is defined as the number of days between randomization and the date of progression (as confirmed by the IRC) or death due to any cause, whichever occurs first. Subjects who had no event (progression or death) will be censored at the day of their last adequate disease assessment. If no baseline or post-baseline assessment is available, the subject will be censored at the date of randomization. If death or PD occurs after 2 or more consecutive missing disease assessments, censoring will occur at the date of the last adequate disease assessment prior to the missed assessments. The use of a new anticancer therapy prior to the occurrence of PD will result in censoring at the date of last adequate disease assessment prior to initiation of new therapy.

Hypothesis testing for comparison between the treatment arms will be performed using a stratified (by randomization stratification factors) log-rank test via SAS Lifetest procedures. For each treatment arm, the median duration of PFS and the proportion of subjects alive and progression-free at 6, 12, 24, and 36 months will be estimated using the Kaplan-Meier method. For each estimate, a 95% confidence interval will be reported. The hazard ratio with 95% confidence interval will be estimated by stratified (by randomization stratification factors) Cox proportional hazards model.

U2-VEN-207

Sensitivity analyses will be conducted, including using investigator assessment of PFS, using different censoring rules (ignoring new anti-cancer therapy, ignoring 2 or more consecutive missing assessments). In addition, the potential impact of COVID-19 on patients for the efficacy results may be included in the sensitivity analysis (censoring all subjects at the last adequate assessment if subject discontinued study or death due to COVID-19). Other sensitivity analyses may be conducted as needed.

11.11.1.2 COMPLETE RESPONSE RATE (PHASE 2)

CR rate is defined as the percent of subjects who achieve a CR or CRi. Estimated CR rate with exact 95% confidence interval based on Clopper-Pearson method will be presented for the Phase 2 component.

11.11.1.3 OVERALL RESPONSE RATE (PHASE 2)

ORR will be determined according to the criteria of the iwCLL (Hallek et al., 2018).

ORR is defined as percent of subjects who achieve CR, CRi, PR or PR-L. Estimated ORR with exact 95% confidence interval based on Clopper-Pearson method will be presented for the Phase 2 component.

11.11.2 SECONDARY EFFICACY OUTCOMES

11.11.2.1 MINIMAL RESIDUAL DISEASE NEGATIVITY

The MRD negativity rate is defined as the proportion of subjects who achieve MRD negative status post-baseline. Subjects who do not have an MRD assessment at any post-baseline visits will be considered non-responders and will be included in the denominator when calculating MRD negativity rate. Estimated MRD negativity rate with exact 95% confidence interval based on Clopper-Pearson method will be presented for the Phase 2 component, while the Phase 3 will utilize a Cochran-Mantel-Haenzel (CMH) test stratified by the randomization factors.

11.11.2.2 DURATION OF RESPONSE

DOR defined as the interval from the first documentation of CR, CRi, PR or PR-L to the earlier of the first documentation of definitive disease progression or death from any cause. This variable will be analyzed using Kaplan-Meier method for responders only. The estimated median DOR with 95% confidence interval will be presented.

11.11.2.3 TIME TO RESPONSE (TTR)

TTR is defined as the interval from enrollment to first documentation of CR, CRi, PR, or PR-L. TTR will be analyzed via Kaplan-Meier method.

11.11.2.4 COMPLETE RESPONSE RATE

For the Phase 3 portion of the study. CR rate will be analyzed using a Cochran-Mantel-Haenzel (CMH) test stratified by the randomization factors. Additional logistic analyses model may be used to assess the impact of demographic and baseline parameters.

11.11.2.5 OVERALL RESPONSE RATE

U2-VEN-207

For the Phase 3 portion of the study, ORR rate will be analyzed using a CMH test stratified by the randomization factors. Additional logistic analyses model may be used to assess the impact of demographic and baseline parameters.

11.11.2.6 OVERALL SURVIVAL

Overall Survival (OS) is defined as the interval from randomization to death from any cause. As subjects are expected to survive for a long time relative to the duration of the study, OS analysis may not be reliable due to heavily censored data. OS data will be censored at the last documented date that the subject is confirmed alive for subjects who withdraw consent or are lost to follow-up prior to the end of the study, and for subjects whose vital status in the study cannot be determined. The Kaplan-Meier estimator for OS will be presented for all subjects in the ITT population. An interim analysis of OS will occur at the time of the PFS analysis, and a final OS analysis will occur 1 year after the PFS analysis.

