4.4 STUDY SITES

This study may be conducted in approximately 125 centers. Enrollment is expected to take approximately 24 months.

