The final primary efficacy analyses for each cohort will be performed when approximately 172 PFS events and 122 PFS events have been observed in the treatment naive and previously treated cohorts,

U2-VEN-207

respectively, where PFS will be tested at the significance level of approximately 0.0462 (two-sided), corresponding to detecting an HR of ≤ 0.74 or less for the treatment naïve cohort and an HR of ≤ 0.70 or less for the previously treated cohort. If necessary, the statistical test level will be adjusted to incorporate the alpha spent at the interim analysis so that the overall type I error rate will be maintained at the 2-sided 0.05 level.

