11.11.4 MULTIPLICITY OF PHASE 3 PART

In the efficacy analyses, the following gatekeeping procedures will be implemented to preserve the overall type I error rate across the primary and secondary endpoints of the Phase 3 part of the study at a 2-sided significance level of 0.05.

The type I error control is applied separately to the two cohorts of the study (the treatment naïve cohort and the previously treated cohort) as they are intended to be conducted and analyzed independently and have independent powering.

The primary endpoint PFS analysis will serve as the gatekeeper for the secondary endpoint analyses, i.e., the primary efficacy hypothesis must be rejected before the efficacy hypotheses for the secondary efficacy endpoints can be evaluated.

The secondary endpoints will be sequentially tested at the 2-sided 0.05 significance level in the following order:

- Complete Response (CR) Rate
- Rate of Undetectable Minimal Residual Disease (uMRD)
- Overall Response Rate (ORR)
- Overall Survival (OS)

If a null hypothesis is not rejected, formal sequential testing will be stopped and only nominal significance will be cited for the remaining secondary endpoints. Note, CR Rate, uMRD, and ORR will only be tested once either at the interim or final analysis depending on the outcome of the PFS analysis.

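### Overall survival is analysed twice, but the visible plan gives it no alpha allocation, so the claimed two-sided 0.05 control is not secured for OS

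*Combined protocol and SAP*

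**What the plan says.** Section 11.11.2.6 sets the OS schedule, with the second look timed from the first: "An interim analysis of OS will occur at the time of the PFS analysis, and a final OS analysis will occur 1 year after". The only OS method it names is an estimate: "The Kaplan-Meier estimator for OS will be presented for all subjects in the ITT population". It gives no test, boundary or level.

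Section 11.11.4 states the purpose of the gatekeeping, which is to "preserve the overall type I error rate across the primary and secondary endpoints of the Phase 3 part of the study" at two-sided 0.05. It adds that "The type I error control is applied separately to the two cohorts of the study". PFS is the gatekeeper, and then "The secondary endpoints will be sequentially tested at the 2-sided 0.05 significance level in the following order": CR rate, uMRD rate, ORR, OS. A closing note says that "CR Rate, uMRD, and ORR will only be tested once either at the interim or final analysis". OS is not in that note.

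Section 11.11.3 treats repeated looks at PFS in full. It has a Lan-DeMets O'Brien-Fleming-type spending function, a one-sided interim level of 0.00618 at 67% of the events, and a final two-sided level of about 0.0462. If needed, "the statistical test level will be adjusted to incorporate the alpha spent at the interim analysis". All of this is written for PFS.

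**The concern.** Every endpoint in the testing order has some protection against repeated testing except OS. PFS has alpha spending, and CR, uMRD and ORR are tested once. OS has two named analyses, a level of 0.05, and neither safeguard. Taken literally, these rules allow an OS claim at 0.05 at the first look and, failing that, another attempt at 0.05 a year later. Two attempts at the full level do not hold the level, so the error-control statement in section 11.11.4 would not be true for OS.

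A false OS claim is what is at stake. Section 11.11.3 expects results to go to health authorities for possible registration, and an OS claim reached through an unallocated second look would be hard to defend there.

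**Working it through.** **Inputs from the protocol.** Two OS looks, one year apart (11.11.2.6). Two-sided 0.05 for each secondary endpoint, controlled separately by cohort (11.11.4). PFS interim at 67% information, with levels 0.00618 one-sided and 0.0462 two-sided (11.11.3). Enrollment: "Enrollment is expected to take approximately 24 months" (4.4).

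**Inputs not given, so assumed.** The OS information fraction *t* at the first look (deaths then divided by deaths at the final OS analysis), annual mortality, and the calendar time of the PFS analysis.

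**Step 1: reproduce the plan's own PFS levels.** The one-sided spending function is α(t) = 2 − 2Φ(z/√t), with z = Φ⁻¹(1 − 0.0125) = 2.241. At t = 0.67, α = 0.00618. Solving the bivariate normal with correlation √t for a total of 0.025 gives a final two-sided level of 0.0462. Both match the protocol. With exact event counts the interim levels are 0.00612 (115/172) and 0.00626 (82/122), and the final level is again 0.0462.

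**Step 2: two OS looks at the full level.** Under no OS difference, Z₁ and Z₂ are standard normal with correlation √t. The two-sided error is P(|Z₁| > 1.96 or |Z₂| > 1.96). The error favouring U2-V is P(Z₁ > 1.96 or Z₂ > 1.96).

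| t at first look | Two-sided error | Error favouring U2-V |
|---|---|---|
| 0.3 | 0.0893 | 0.0447 |
| 0.5 | 0.0831 | 0.0416 |
| 0.6 | 0.0796 | 0.0398 |
| 0.7 | 0.0756 | 0.0378 |
| 0.8 | 0.0709 | 0.0354 |
| 0.9 | 0.0648 | 0.0324 |
| 0.95 | 0.0604 | 0.0302 |

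The nominal values are 0.05 and 0.025. A simulation of 4 million trials gives 0.0797, 0.0755 and 0.0708 at t = 0.6, 0.7 and 0.8.

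**Step 3: which fractions are plausible?** Assume uniform accrual over 24 months and exponential survival with monthly hazard λ. The expected proportion dead at month T ≥ 24 is D(T) = 1 − [e^(−λ(T−24)) − e^(−λT)]/(24λ), and t = D(T)/D(T+12).

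Worked case, 5% annual mortality and PFS analysis at month 36:
- λ = −ln(0.95)/12 = 0.004274, so 24λ = 0.10259.
- D(36) = 1 − (0.95000 − 0.85738)/0.10259 = 0.0971.
- D(48) = 1 − (0.90250 − 0.81451)/0.10259 = 0.1422.
- t = 0.0971/0.1422 = 0.683, and the two-sided error is 0.0763.

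| PFS analysis (month), 5% annual mortality | t | Two-sided error |
|---|---|---|
| 24 | 0.511 | 0.0828 |
| 30 | 0.614 | 0.0791 |
| 36 | 0.683 | 0.0763 |
| 48 | 0.768 | 0.0725 |
| 60 | 0.820 | 0.0698 |

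With annual mortality from 2% to 15%, t runs from 0.606 to 0.643 at month 30 and from 0.808 to 0.858 at month 60. Over months 30 to 60 this gives t of 0.61 to 0.86 and an error of 6.8% to 7.9%. At month 24, t is 0.50 to 0.53 and the error 8.2% to 8.3%.

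**Step 4: levels that would hold 0.05.** The same type of spending function applied to OS gives these two-sided levels, each with an overall two-sided error of 0.050.

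| t | First look | Final look |
|---|---|---|
| 0.6 | 0.0076 | 0.0476 |
| 0.7 | 0.0148 | 0.0455 |
| 0.8 | 0.0244 | 0.0429 |

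**The case against.** The strongest reply is that the inflation needs a premise the protocol never states: a formal OS test at 0.05 at both looks. Section 11.11.2.6 names only a Kaplan-Meier estimate and warns that OS may be unreliable because of heavy censoring. That fits a descriptive first look and a single later test, with no inflation. This stands as a possible reading. It is not secured, because section 11.11.4 lists OS for formal testing, omits it from the single-test note, and does not say which look carries the test.

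Second, the answer may lie in text not seen here. Section 11.1 is blank in this copy, the Version 4.0 amendment summary says that section gained wording on the interim analysis, and section 11 refers details to the SAP. This also stands, and it limits the finding to the visible text. But section 11.11.4 is visible, makes the error-control claim and sets out the rules for the other secondary endpoints, so the OS rule belongs there.

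Third, mortality and timing are assumed, and the 24 months is a study-level figure applied to each of two separately enrolled cohorts. The exact percentage is therefore uncertain. The direction is not: the error exceeds 0.05 at every fraction tried.

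Fourth, the reach is narrow, since OS is tested only after four rejections. That bears on severity, but not on whether the stated control holds. The censoring warning applies to OS generally, so it is not an argument against the first look alone.

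**Conclusion.** The concern holds for the visible text. The plan claims two-sided 0.05 control across primary and secondary endpoints in each cohort, yet its rules do not deliver that for OS if both scheduled looks are tested at 0.05. The OS error would then be about 7% to 8% at assumed information fractions of 0.6 to 0.8. These figures are conditional on the OS null being true and on PFS, CR, uMRD and ORR all having been rejected in that cohort. If the first look is descriptive there is no inflation, but the text needs to say so. The PFS conclusion and the earlier secondary tests are untouched. This should be fixed, but it does not threaten the primary result.

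**What to change.** Amend sections 11.11.2.6 and 11.11.4, and the SAP to match, with one of two choices:

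1. Give OS its own Lan-DeMets O'Brien-Fleming-type spending within each cohort. Base it on deaths observed divided by deaths planned at the final OS analysis, and state the planned number of deaths. Step 4 of the working gives example levels.
2. State that the OS look at the PFS analysis is descriptive and that OS is tested once, at the final OS analysis, at two-sided 0.05.

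In either case, name the OS test. Also say whether the PFS analysis that triggers the first OS look and starts the one-year clock is the interim or the final one when PFS succeeds at its interim. If OS could be tested at the PFS interim, at the PFS final and a year later, three looks at 0.05 would give about 9.6% to 10.4% (assumed fractions of 0.4 to 0.5 and 0.7 to 0.8 at the first two looks).

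The cost is wording only, with no change to sample size, visits or treatment. Under option 1, at 70% information, the first-look level falls from 0.05 to about 0.015 and the final level to about 0.046. Under option 2 no early OS claim is possible, but the final test keeps the full 0.05.
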